### 10.5.1 Adverse Events

For analysis purposes, AEs will be classified as TEAEs, or post-treatment AEs.

- **TEAE:** any AE that increased in severity or that was newly developed during the Treatment-emergent Period of the Current Study Period.
- **Post-treatment AE:** any AE that increased in severity or that was newly developed after the end of the Treatment-emergent Period of the Current Study Period.

For AEs with missing or partial start dates, if there is no clear evidence that the AEs started before or after study treatment, then the AEs will be classified as TEAEs. Details for imputing missing or partial start dates of AEs are described in [Appendix E](#).

TEAE summaries will be presented using number and percentages of subjects for the Current Study Period based on 116 Safety Set.

An overview of the TEAE profile will be provided, including total number of TEAEs, with number and percentage of subjects for the following categories: 1) all TEAEs; 2) Grade 3/4 TEAEs; 3) TEAEs by relationship; 4) TEAEs by maximum severity; 5) TEAEs leading to treatment interruption; 6) TEAEs leading to treatment discontinuation; 7) serious TEAEs; 8) serious TEAEs related to study drug; and 9) TEAEs leading to death.

AE summary tables will be presented for TEAEs only and will include the following:

- All TEAEs
- Grades 3/4 TEAEs
- TEAEs by relationship to study drug
- TEAEs by maximal severity
- TEAEs leading to treatment interruption
- TEAEs leading to treatment discontinuation
- Serious TEAEs
- Serious TEAEs related to study drug
- TEAEs leading to death
- Frequently reported TEAEs ( $\geq 5\%$  at the preferred term level for the overall column)

Summaries will be presented by MedDRA SOC and PT using frequency counts and percentages (i.e., number and percentage of subjects). When summarizing the number and percentage of subjects with an event, subjects with multiple occurrences of the same AE or a continuing AE will be counted once, only the maximum severity level will be presented in the severity summaries, and the worst/highest relationship level in the relationship summaries.

In addition, listings containing individual subject data for all TEAEs leading to treatment interruption, TEAEs leading to treatment discontinuation, deaths, and SAEs will be provided separately. All AEs, including pre- and post-treatment AEs, will be presented in individual subject data listings.

#### **Analysis of AEs of special interest (AESI):**

Three categories of AESI are defined: elevated transaminases, respiratory symptom AESI and respiratory event AESI. Treatment-emergent AESIs will be summarized by

- Number and percentage of subjects by PT
- Number and percentage of subjects by maximum severity
- Summary of duration of events (days) with descriptive summary
- Summary of time-to-first onset (relative to first dose date)
- Number and percentage of subjects with 1) TEAE leading to treatment interruption; 2) TEAE leading to treatment discontinuation; 3) serious TEAEs; 4) related serious TEAEs; and 5) TEAE leading to death.

#### **10.5.2 Clinical Laboratory**

For the laboratory measurements, the raw values and change from parent study baseline of the continuous hematology and chemistry results will be summarized in SI units at each visit in the Current Study Period (including all measurements from Study 116) for the overall group based on the 116 Safety Set.

For hematology and chemistry, the number and percentage of subjects with abnormal low (<lower limit of normal [LLN]) value and with abnormal high (>ULN) value at each scheduled time point in the Current Study Period will be summarized for the overall group based on the 116 Safety Set.

The number and percentage of subjects meeting the defined threshold criteria during the Treatment-emergent Period of the Current Study Period will be provided based on the 116 Safety Set. The threshold criteria are provided in [Appendix F](#).

Results of urinalysis will be listed in individual subject data listings only. In addition, a listing containing individual subject hematology, chemistry, and coagulation values outside the reference ranges will be provided. This listing will include data from scheduled and unscheduled time points.

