# 8.2 Exclusion Criteria (Treatment Cohort Only)

- 1. Prematurely discontinued LUM/IVA treatment in Study 115B.
- 2. History of any comorbidity or laboratory abnormality that, in the opinion of the investigator, might confound the results of the study or pose an additional risk in administering LUM/IVA to the subject (e.g., cirrhosis with portal hypertension).
- 3. History of drug intolerance or other serious reactions to LUM/IVA in Study 115B that would pose an additional risk to the subject in the opinion of investigator, and which should be discussed with the Vertex medical monitor.
- 4. Subjects with a history of allergy or hypersensitivity to LUM/IVA.
- 5. Liver function test (LFT) abnormality meeting criteria for LUM/IVA treatment interruption at the completion of Study 115B, for which no convincing alternative etiology is identified.
- 6. QTc value at the completion of Study 115B that would pose an additional risk to the subject in the opinion of investigator, and which should be discussed with the Vertex medical monitor (e.g., remained above the threshold value [>45 msec from baseline or >500 msec] on

- repeated measurement or was noted on 2 or more occasions with no identified alternative etiology for the increased QTc).
- 7. History of poor compliance with LUM/IVA and/or procedures in Study 115B as deemed by the investigator.
- 8. Participation in an investigational drug trial (including studies investigating LUM and/or IVA) other than Study 115B. NOTE: participation in a non-interventional study is permitted (including observational studies, registry studies, and studies requiring blood collections without administration of study drug).

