#### **Elevation of Liver Function Test Parameters** 11.6.3

#### Mandatory Liver Function Testing

Liver function testing (alanine aminotransferase [ALT], aspartate aminotransferase [AST], gamma-glutamyl transferase [GGT], alkaline phosphatase [ALP], and total bilirubin) must be performed while subjects are receiving LUM/IVA treatment (see Table 3-1 and Section 11.6.2). These blood samples should be processed and shipped immediately per the Laboratory Manual.

Subjects with new ALT or AST elevations of  $\ge 3 \times \text{upper limit of normal (ULN)}$  and clinical symptoms will be followed closely, including repeat confirmatory testing performed by the central laboratory within 48 to 72 hours of the initial finding and subsequent close monitoring of ALT and AST levels, as clinically indicated. If a subject cannot return to the site for liver function testing, a local laboratory may be used. Elevations in LFTs (ALT or AST  $\geq 3 \times ULN$ ) at the local laboratory must be reported immediately to the medical monitor AND the subject must

have the tests repeated and sent to the central laboratory as soon as possible (ideally within 48 to 72 hours).

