### **Study Drug Interruption**

LUM/IVA administration must be interrupted immediately, and the Vertex medical monitor or designee must be notified if any of the following criteria is met:

- ALT or AST  $> 8 \times ULN$
- ALT or AST  $\geq$ 5 × ULN for more than 2 weeks
- ALT or AST  $\ge 3 \times ULN$  in association with total bilirubin  $\ge 2 \times ULN$  and/or clinical jaundice

A thorough investigation of potential causes should be conducted, and the subject should be followed closely for clinical progression.

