## 13.1.1.2 Clinically Significant Assessments

Study assessments including laboratory tests, ECGs, PEs, and vital signs will be assessed and those deemed to have clinically-significant worsening from baseline will be documented as an AE. When possible, a clinical diagnosis for the study assessment will be provided, rather than the abnormal test result alone (e.g., urinary tract infection, anemia). In the absence of a diagnosis, the abnormal study assessment itself will be listed as the AE (e.g., bacteria in urine or decreased hemoglobin).

An abnormal study assessment is considered clinically significant if the subject has 1 or more of the following:

- Concomitant signs or symptoms related to the abnormal study assessment
- Further diagnostic testing or medical/surgical intervention
- A change in the dose of study drug or discontinuation from the study

Repeat testing to determine whether the result is abnormal, in the absence of any of the above criteria, does not necessarily meet clinically significant criteria. The determination of whether the study assessment results are clinically significant will be made by the investigator.

A laboratory value that is Grade 4 will not automatically be an SAE. A Grade 4 laboratory value will be an SAE if the subject's clinical status indicates a life-threatening AE.

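### The ALT, AST and total bilirubin count tables carry no pre-drug status, so they cannot separate elevations present before any LUM/IVA from later ones

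*SAP*

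**What the plan says.** SAP 10.5.2 plans three laboratory tables for Study 116:

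- continuous values and change from the Study 115B baseline, by visit;
- counts below LLN or above ULN, by visit;
- threshold counts: "The number and percentage of subjects meeting the defined threshold criteria during the Treatment-emergent Period of the Current Study Period will be provided".

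In Table 13-5 (SAP Appendix F) the ALT, AST and total bilirubin rows, alone and combined, are multiples of ULN without a baseline term. The chemistry windows in SAP Appendix C, Table 13-3, open after Study 116 Day 1. Out-of-range values are listed by subject.

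The other route is adverse event reporting. Protocol 13.1.1.2 says of study assessments that "those deemed to have clinically-significant worsening from baseline will be documented as an AE", and adds: "The determination of whether the study assessment results are clinically significant will be made by the investigator". SAP 10.5.1 counts only new or worsened events as TEAEs. It then singles out some for closer summary: "Three categories of AESI are defined: elevated transaminases, respiratory symptom AESI and respiratory event AESI".

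**The concern.** Long-term safety is the primary objective and the Treatment Cohort has no concurrent control, so the value before any drug is each child's natural reference. SAP 10.1 defines baseline that way. For liver tests, however, that baseline enters only a group-level summary of change, which cannot say whether a particular child's threshold crossing was there beforehand.

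Elsewhere the SAP does use subject-level baseline status. Creatinine and hemoglobin have baseline-relative criteria in Table 13-5, and baseline shifts are planned for ECG evaluation (10.5.3), pulse oximetry (10.5.5) and FE-1 (10.3.2.7).

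At stake is how a row such as ALT or AST above 3x ULN is read. If some counted children were already above the cut-off before LUM/IVA, the row overstates what arose later, and a reader of the tables cannot tell.

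**Working it through.** **1. Which planned outputs can classify a child's elevation as present before drug?**

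| Output | Uses Study 115B baseline | Classifies the child |
|---|---|---|
| Change from baseline, by visit (SAP 10.5.2) | yes | no, group statistics |
| Counts above ULN, by visit (SAP 10.5.2) | no | no |
| Threshold counts (Table 13-5, liver rows) | no | no |
| TEAE and AESI tables (SAP 10.5.1) | indirectly, through the reporting rule | only if reported as an AE |
| Subject listings | not stated | by hand, if baseline is shown |

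Chemistry is drawn on Study 116 Day 1 (Protocol Table 3-1), but that follows the 24-week treatment period and planned 2-week washout of Study 115B. It is not a pre-drug value, and Table 13-3 has no window for it.

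**2. What the AE route leaves uncovered.** Protocol 13.1.1.2 treats a result as clinically significant if there are related symptoms, further testing or intervention, or a change in dose or discontinuation. Protocol 11.6.3 requires interruption, and calls for investigation, at >8x ULN, at >=5x ULN for more than 2 weeks, and at >=3x ULN "in association with total bilirubin" of >=2x ULN and/or jaundice. Those cases should reach the AE tables. The remainder is mainly asymptomatic ALT or AST elevation with no work-up or interruption, and isolated bilirubin elevation, which is outside the AESI categories.

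**3. Entry rules.** The Study 116 criteria do not describe the pre-drug baseline. Protocol 8.2 criterion 5 excludes an LFT "abnormality meeting criteria for LUM/IVA treatment interruption at the completion of Study 115B", which is after treatment, and only where no convincing alternative cause is found. Criterion 2, "History of any comorbidity or laboratory abnormality that, in the opinion of the investigator, might confound the results of the study", is discretionary and sets no multiple. The Study 115B entry criteria are not in the documents.

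**4. Scale.** The plan's own figure reproduces: 56 x (1 - 0.10) = 50.4, stated as 50. Taking 50 as the size of the 116 Safety Set (assumed), one child is 1/50 = 2.0 points.

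**5. Illustration (all counts assumed).** Suppose 4 of 50 are counted above 3x ULN, k of those 4 were also above it before drug, and m children in all were above it before drug. The rate among children not above it before drug is (4 - k)/(50 - m).

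| k | m = k | m = k + 3 |
|---|---|---|
| 0 | 4/50 = 8.0% | 4/47 = 8.5% |
| 1 | 3/49 = 6.1% | 3/46 = 6.5% |
| 2 | 2/48 = 4.2% | 2/45 = 4.4% |
| 3 | 1/47 = 2.1% | 1/44 = 2.3% |
| 4 | 0/46 = 0% | 0/43 = 0% |

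Here k drives the result; the denominator moves it by at most 0.5 points. The table takes one baseline draw as settling pre-drug status, which suits persistent elevation only.

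**6. What a shift table can remove.** Take a child who exceeds the cut-off on each draw with probability p, independently and with no drug effect (p assumed). Seven on-treatment chemistry draws are scheduled: Day 15 and Weeks 12, 24, 36, 48, 72 and 96.

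- Counted in Table 13-5: 1 - (1-p)^7.
- Shown as a shift from below the cut-off: (1-p)(1 - (1-p)^7).
- One draw against one draw: p(1-p).

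| p | Table 13-5 | Shift | One against one |
|---|---|---|---|
| 0.05 | 30.2% | 28.7% | 4.8% |
| 0.1 | 52.2% | 47.0% | 9.0% |
| 0.2 | 79.0% | 63.2% | 16.0% |
| 0.5 | 99.2% | 49.6% | 25.0% |
| 1 | 100% | 0% | 0% |

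The shift removes a fraction p of such cases: all of a persistent elevation, little of one that comes and goes.

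**The case against.** The strongest case against is that this is a display preference. Absolute ULN cut-offs are conventional: Table 13-5 attributes most of its liver rows to FDA guidance on drug-induced liver injury, and they use the same scale as the interruption rules. Serious elevations should reach the AE tables. Change from baseline is summarized, listings exist, and few children are involved. A shift from a single baseline draw removes little of a fluctuating elevation. It also measures change from pre-drug status, so an elevation that began during Study 115B would appear as a shift without being new in Study 116.

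Much of this stands. It confines the point to the remainder in step 2, rules out replacing the ULN counts, and is why the fix includes a Day 1 row and a footnote. It does not remove the gap. A group mean cannot classify a child, SAP 10.5.2 does not say that the out-of-range listing shows the Study 115B baseline, and a persistent pre-drug elevation is exactly what a shift identifies.

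Three stronger readings are tempting but unsupported:

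- **The protocol's follow-up rule requires a baseline condition.** Protocol 11.6.3 does speak of "Subjects with new ALT or AST elevations of" at least 3x ULN, but only together with clinical symptoms. Symptoms related to the result meet the clinical-significance criteria, so those cases belong to the AE route and say nothing about unreported elevations.
- **The SAP dropped a promised laboratory shift.** Protocol 12.3.4.2 refers to categorical change but leaves the criteria to the SAP and names no shift.
- **The Study 116 counts are inflated.** Nothing in the documents shows that any child had raised liver tests before drug.

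**Conclusion.** The point holds in a limited form. As planned, the summary tables cannot separate ALT, AST or total bilirubin elevations present before any LUM/IVA from later ones. This matters mainly for the elevations least likely to be reported as AEs. The finding about the tables rests on reading SAP 10.5.2, Table 13-5 and Table 13-3, and needs no assumption.

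The size is unknown and may be zero. Each affected child would be 2.0 points if the 116 Safety Set is about 50. The span from 8.0% to 0% in the illustration shows what the tables could not distinguish, not what is expected. Sampling error at this size is also wide: the exact 95% interval for 4/50 is 2.2% to 19.2%. This is an inexpensive improvement to reporting of the primary objective. It does not invalidate the planned counts.

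**What to change.** In SAP 10.5.2, keep Table 13-5 unchanged and make three additions.

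1. **By-visit table of values above ULN**, for ALT, AST and total bilirubin: add a Study 115B baseline row and a Study 116 Day 1 predose row. The first gives pre-drug status; the second shows what was already present on entry to Study 116. Where Day 1 coincides with the Study 115B Safety Follow-up Visit and sampling is not repeated, take the value from that visit.
2. **One compact shift** from Study 115B baseline category to worst treatment-emergent category in Study 116, with missing baseline shown separately:
   - ALT or AST (higher multiple): baseline <=ULN, >ULN to <=3x, >3x; worst <=ULN, >ULN to <=3x, >3x to <=5x, >5x to <=8x, >8x (3 x 5 = 15 cells).
   - Total bilirubin: baseline <=ULN, >ULN to <=1.5x, >1.5x; worst <=ULN, >ULN to <=1.5x, >1.5x to <=2x, >2x (3 x 4 = 12 cells).
   - Exclude the Day 1 predose sample from the worst category, since the treatment-emergent period is defined by first dose date.
3. **Footnote**: the shift is relative to pre-drug status and does not mean new in Study 116. It compares one baseline draw with the worst of 7 or more, so it identifies persistent pre-existing elevation but removes only a fraction p of fluctuating elevation (for example 52.2% to 47.0% at p = 0.1). Read it beside the by-visit rows.

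The cost is SAP wording, two rows and one small table. Study 115B baseline chemistry is already needed for change from baseline, so no new data are collected. SAP section 4 allows the change before database lock; afterwards it would be documented in the clinical study report.

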#### **10.5.3 Electrocardiogram**

For the ECG measurements, a summary of raw values and change from parent study baseline will be provided at each scheduled time point of the Current Study Period (including all measurements from Study 116) based on the 116 Safety Set for the overall group, for the following standard digital ECG measurements: RR, PR, QT, and QT corrected for HR (QTc) intervals (Fridericia's correction [ $QTcF = QT/RR^{1/3}$ ], QRS duration, and HR. In addition, the mean value at each time point will be plotted for QTcF.

The number and percentage of subjects meeting the defined threshold criteria during the Treatment-emergent Period of the Current Study Period will be summarized based on 116 Safety Set. The threshold criteria are provided in [Appendix F](#).

The number and percentage of subjects with shift changes from parent study baseline (normal/missing, not clinically significant, and potentially clinically significant according to overall ECG evaluation) to the worst ECG evaluation during the Treatment-emergent Period of the Current Study Period will be summarized based on 116 Safety Set.

Listings will be provided for the ECG measurements.

#### 10.5.4 Vital Signs

For the vital signs measurements, the raw values and change from parent study baseline values will be summarized at each scheduled time point of the Current Study Period (including all measurements from Study 116) based on the 116 Safety Set: systolic and diastolic blood pressure (mm Hg), body temperature (°C), pulse rate (beats per minute), respiratory rate (breaths per minute), as well as weight, stature, and BMI.

The number and percentage of subjects meeting the defined threshold criteria during the Treatment-emergent Period of the Current Study Period will be summarized based on 116 Safety Set. The threshold criteria are provided in [Appendix F](#).

Potentially abnormal SBP and DBP by their percentiles adjusted for sex, age and stature will be provided, including

- Number and percentage of subjects with categories:  $\geq 90\%$ - $<95\%$ ,  $\geq 95\%$ - $<99\%$  + 5 mmHg and  $\geq 99\%$  + 5 mmHg during the treatment-emergent period of the Current Study Period
- Number and percentage of subjects with SBP and DBP percentiles  $\geq 95\%$  once and twice during the treatment-emergent period of the Current Study Period
- Number and percentage of subjects with SBP and DBP percentiles  $\geq 95\%$  at each visit in the Current Study Period

The stature adjustment will be based on stature-for-age z-scores and their corresponding percentiles using the standard normal distribution ([Appendix H](#)). The stature percentiles will be further mapped per the following rules:

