## 9 ANALYSIS PERIODS

### 9.1 Current Study Period

The **Current Study Period** starts from the first dose date of study drug in Study 116 to the last day in Study 116.

The **Treatment-Emergent Period for the Current Study Period** starts on or after the first dose date of study drug in Study 116 to 14 days (inclusive) after the last dose of study drug in Study 116 or up to the last day in Study 116, whichever occurs first.

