### 9.2 Cumulative Study Period

The **Cumulative Study Period** starts from the first dose date of study drug in Study 115B to the last day in Study 116, regardless of

- 1) the planned 2-week Washout Period in Study 115B; and/or
- 2) the rollover gap between Study 115B and Study 116 (if any).

For subjects not enrolled in Study 116, the Cumulative Study Period will start from the first dose date of study drug in Study 115B to the last day in Study 115B.

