### **10.3.2.7 Absolute Change in FE-1 Levels From Baseline**

The raw values and absolute change from parent study baseline in FE-1 will be summarized at each scheduled visit during the Current Study Period for the overall group based on the 116 FAS. In addition, the number and percentage of subjects with shift changes from parent study baseline [ $<15 \mu\text{g/g}$ ,  $\geq 15 \mu\text{g/g}$  to  $<200 \mu\text{g/g}$  (consistent with pancreatic insufficient), and  $\geq 200 \mu\text{g/g}$  (consistent with pancreatic sufficient)] at each visit and at any visits ( $<15 \mu\text{g/g}$ ,  $\geq 15 \mu\text{g/g}$  to  $<200 \mu\text{g/g}$ , and  $\geq 200 \mu\text{g/g}$ ) in the Current Study Period will be provided. A spaghetti plot of the FE-1 values will also be provided including Study 115B baseline, and visits in the Current Study Period.

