### **Treatment Cohort**

Evaluating safety of long-term LUM/IVA treatment in the Treatment Cohort is the primary objective of this study. The overall safety profile of study drug will be assessed in terms of the following safety and tolerability endpoints:

- Treatment-emergent adverse events (TEAEs)
- Clinical laboratory values (serum chemistry, hematology, coagulation studies and urinalysis)
- ECGs (standard 12-lead)
- Vital signs
- Pulse oximetry
- OEs
- Spirometry (subjects  $\geq 3$  years age at screening in Study 115B)

The safety analysis will be performed based on the 116 Safety Set for the Current Study Period. Only descriptive summary statistics of safety data will be provided (i.e., no statistical hypothesis testing will be performed). All listings will be provided based on the 116 All Subjects Set.

The safety summaries described in the sections below will be performed for the Treatment Cohort based on the Current Study Period only.

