### **10.5.5 Pulse Oximetry**

For the pulse oximetry measurements, a summary of raw values and change from parent study baseline will be provided at each scheduled time point in the Current Study Period for the percent of oxygen saturation based on the 116 Safety Set.

The number and percentage of subjects with shift changes from parent study baseline (normal/missing and low according to the reference range) to the lowest percent of oxygen saturation during the Treatment-emergent Period of the Current Study Period, will be summarized based on the 116 Safety Set.

Listings will be provided for the pulse oximetry measurements.

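### SAP 10.5.4 (minor): no blood pressure percentile is planned at the Study 115B baseline, so the percentile counts cannot separate high readings that predate treatment from new ones

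*SAP*

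**What the plan says.** SAP 10.5.4 plans three outputs for systolic and diastolic pressure (SBP, DBP): "Potentially abnormal SBP and DBP by their percentiles adjusted for sex, age and stature will be provided, including" the number of children in each percentile category, the number at or above the 95th percentile once and twice, and the number at or above it at each visit. The first two are limited to the treatment-emergent part of the Current Study Period, and the third to visits in that period. The Current Study Period "starts from the first dose date of study drug in Study 116 to the last day in Study 116". SAP 10.5 adds that "The safety summaries described in the sections below will be performed for the Treatment Cohort based on the Current Study Period only".

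Baseline (SAP 10.1) is the last value before the first Study 115B dose, so it lies outside every percentile table. Treatment Cohort children have completed 24 weeks of treatment by then (protocol 8.1).

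The comparison with baseline that does exist for blood pressure is in raw units: "the raw values and change from parent study baseline values will be summarized at each scheduled time point of the Current Study Period". Mean plots, vital-sign listings and a listing of children with potentially abnormal readings are also planned. Neither the baseline characteristics in SAP 10.2.2 nor the vital-sign thresholds in Table 13-7 include a blood pressure item.

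Elsewhere the SAP does link abnormal findings to baseline:
- ECG (10.5.3): "The number and percentage of subjects with shift changes from parent study baseline (normal/missing, not clinically significant, and potentially clinically significant" categories, to the worst evaluation.
- Pulse oximetry (10.5.5): "shift changes from parent study baseline (normal/missing and low according to the reference range) to the lowest percent of oxygen saturation".
- FE-1 (10.3.2.7): "In addition, the number and percentage of subjects with shift changes from parent study baseline".

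**The concern.** Safety is the primary endpoint and there is no control arm, so the pre-treatment value is the only untreated reference for these children. The percentile tables are also the only planned tabulated counts of abnormal blood pressure. A reader who sees a number of children at or above the 95th percentile will want to know how many were there before the first dose, and these tables cannot say.

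Raw change from baseline is not a full substitute. It is a group summary, so it does not show how many children were already high. It also rises with growth over about 2.5 years, which is the reason for adjusting by sex, age and stature at all.

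**Working it through.** **1. The earliest percentile available.** Vital signs are taken on Study 116 Day 1 before the dose and 1, 2 and 4 hours after it (Table 3-1, footnote h). Appendix C assigns the post-dose readings to their nominal visit, so the by-visit table can start on Day 1 post-dose and run to Week 96. Day 1 follows 24 weeks of treatment and "the planned 2-week Washout Period in Study 115B". It is off-drug or nearly so, but it is not pre-treatment.

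**2. Number of readings.** For a child who completes: 3 (Day 1 post-dose) + 1 (Day 15) + 8 (Weeks 12 to 96) = 12. For a child who stops after Week 60: 3 + 1 + 5 = 9. Any early-termination or follow-up visit would add to these.

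**3. Number of children.** The SAP expects 50; 56 × (1 − 0.10) = 50.4, which agrees.

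**4. Model (assumed, not from the documents).** SBP only, no drug effect. Each reading is a Normal z-score with mean μ and variance 1, and any two readings in a child have correlation ρ. The baseline is one further reading of the same kind. Once and twice are read as at least once and at least twice. Given the child's level b, the chance of a high reading is

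p(b) = Φ((μ + √ρ·b − 1.645)/√(1−ρ)).

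With m readings, averaging over b:
- once: E[A], where A = 1 − (1−p)^m
- twice: E[B], where B = A − m·p·(1−p)^(m−1)
- share already high at baseline: E[p·A]/E[A] and E[p·B]/E[B]
- crossing at least once, given below 95% at baseline: E[(1−p)·A]/E[1−p]

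**5. Results at ρ = 0.3 / 0.5 / 0.7.**

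| Quantity (%) | 12 readings, μ = 0 | 9 readings, μ = 0 | 12 readings, μ = 0.5 |
|---|---|---|---|
| At least once | 34.2 / 27.0 / 19.9 | 28.8 / 23.3 / 17.7 | 61.2 / 50.0 / 38.8 |
| At least twice | 14.1 / 13.4 / 11.8 | 10.1 / 10.4 / 9.8 | 37.2 / 32.2 / 27.0 |
| Already high, of once | 10.0 / 14.6 / 21.9 | 10.7 / 15.8 / 23.7 | 17.7 / 22.5 / 30.2 |
| Already high, of twice | 15.4 / 22.6 / 32.2 | 16.9 / 25.2 / 35.6 | 22.9 / 30.1 / 39.8 |
| Crosses once if below 95% at baseline | 32.4 / 24.3 / 16.4 | 27.1 / 20.7 / 14.2 | – |

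The last column is a group that sat 0.5 SD above the norms before treatment.

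**6. In children, of 50 with 12 readings.** At μ = 0, counted once and already high: 50 × 0.342 × 0.100 = 1.7 to 50 × 0.199 × 0.219 = 2.2. Counted twice and already high: 50 × 0.141 × 0.154 = 1.1 to 50 × 0.118 × 0.322 = 1.9. At μ = 0.5 the same products give 5.4 to 5.9 and 4.3 to 5.4.

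**7. One by-visit rate, two readings of it.** With μ = 0 a single visit gives 5.0% at or above the 95th percentile; with μ = 0.5 it gives 12.6%, about 6 of 50. A 12.6% rate at Day 15 fits either an offset of 0.5 SD that predates treatment or a true rise of 0.5 SD from the norms.

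**8. Growth in the raw change.** Day 15 is about 24 + 2 + 2 = 28 weeks after the Study 115B baseline and Week 96 is 24 + 2 + 96 = 122 weeks, if there is no rollover gap. At an assumed 1 to 2 mmHg per year, with 52.18 weeks per year, growth alone adds 0.5 to 1.1 mmHg at Day 15 and 2.3 to 4.7 mmHg at Week 96.

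**The case against.** **Other outputs cover much of this.** Raw change from baseline is planned, and at Day 15 it carries little growth, so it would help tell a group-wide rise from a pre-existing offset. Flagged children are listed, and clinically significant worsening of vital signs from baseline is recorded as an adverse event (protocol 13.1.1.2). This stands in part. None of it gives the number of children already high, and the SAP does not say that the listing shows a baseline percentile.

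**The inconsistency is selective.** Laboratory high and low counts (10.5.2), ALT and AST thresholds and absolute QTc limits (Appendix F) also have no split by baseline, although elevated transaminases are an event of special interest. This stands. The contrast with ECG, pulse oximetry and FE-1 supports the point only in part.

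**The gain is small.** If the children match the norms, the split concerns about 2 of 50 in the once count and 1 to 2 in the twice count. One baseline reading is noisy, and many children below 95% at baseline would cross later by chance. This stands and keeps the point minor. It does not remove it, because the change is almost free and the number concerned is larger if the group starts above the norms.

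**Unseen sources.** Study 115B may report baseline percentiles; these documents do not show it. Appendix H is not visible and is cited only for stature percentiles.

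**Stronger readings a reader might infer.** One is that the plan has no baseline comparison for blood pressure, or cannot show any rise. The documents do not support that: raw change is summarised, and the by-visit counts can be compared with one another within Study 116. Another is that the SAP drops something the protocol required. The protocol's vital-sign section (12.3.4.4) plans no percentiles, so these tables are an addition.

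**Conclusion.** The point holds as a minor one. The visible SAP text confines every blood pressure percentile count to a period that starts after 24 weeks of treatment, and plans none at the Study 115B baseline.

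Under the stated model, 10% to 22% of children counted once over 12 readings, and 15% to 32% of those counted twice, would already have been high before treatment. With a 0.5 SD pre-treatment offset the shares are 18% to 30% and 23% to 40%. For children who stop after Week 60, with no offset, they are 11% to 24% and 17% to 36%.

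The gap itself is read from the text. Its size rests on the assumed correlation, offset and equal correlation among all readings. If the three Day 1 readings are more alike (assumed correlation 0.8 to 0.9), the twice count over 12 readings stays at 12% to 14%. DBP was not modelled. Confidence is medium, mainly because the size is assumed and the parent study's reporting is unknown.

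**What to change.** In SAP 10.5.4:

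1. Derive the SBP and DBP percentile category at the Study 115B baseline with the same lookup.
2. Add that baseline as a row, with its n, to the by-visit table of children at or above the 95th percentile.
3. Split the category counts and the once and twice counts by whether the child was already at or above the 95th percentile at baseline (yes, no, missing).
4. State that the no row is not a count of drug-related cases. With no drug effect, 16% to 32% of children below 95% at baseline would still cross at least once over 12 readings, and the baseline is a single noisy reading.

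A full shift table or a z-score change is optional. Intervals will be wide at this size: 3 of 50 has an exact 95% CI of 1.3% to 16.5%, and 6 of 50 has 4.5% to 24.3%.

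The cost is SAP wording and a few table rows. Age, sex and stature-for-age z-score at the Study 115B baseline are already summarised (10.2.2), baseline SBP and DBP are needed for the raw change, and the lookup is already specified. No new data are collected.
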